## Background and Introduction

---

Proper recovery from exercise training is necessary for training adjustments to occur and for performance to be maintained or improved. Dietary amino acid (the ‘building blocks’ of protein) intake has long been known to be important in the recovery process in order to repair damaged proteins and create new proteins that are important to athletic training and performance (Trommelen & Van Loon, 2016). Muscle recovery is regulated, in part, by nutrient availability, hormones, and inflammation, and is needed for improving a muscle’s ability to perform well. Because diet directly affects nutrient availability and sleep influences hormones and inflammation, diet and sleep are critical health behaviors involved in muscle recovery. Sleep loss can worsen inflammation (Thomas, Motivala, Olmstead, & Irwin, 2011). Protein supplementation and whey protein in particular, is a common sports nutrition strategy for making new proteins in combination with resistance exercise training (Cermak, Res, de Groot, Saris, & van Loon, 2012). During a soccer game, different efforts of exercise are important in raising sport performance. Protein supplementation has been shown to increase new proteins in cells in already trained muscles (Kritikos et al., 2021; Wilkinson et al., 2008). There is also an important link between the greatest amount of oxygen someone can use by their muscles (VO2max) and distance covered by players during a soccer match (Hoff, 2005). Evidence also suggests adding protein after a rigorous session of long-lasting exercise may reduce the muscle’s muscular damage and muscle soreness created by the exercise session (Saunders, Kane, & Todd, 2004; Saunders, Luden, & Herrick, 2007; Valentine, Saunders, Todd, & Laurent, 2008). It is also important for soccer players to have a strong lower-body muscles to perform at competing levels. Protein supplementation may further increase muscle growth with resistance training exercise. This is of help to soccer players who may see increases in sport performance during a game with protein supplementation. One study showed a significant increase in lower-body strength with a protein supplement taken for 10-weeks (Willoughby, Stout, & Wilborn, 2007). However, less is known about the role of whey protein supplementation on outcomes of interest to team sport athletes. Unlike resistance training or long-distance running, team sports (such as soccer) require a mixture of alternating high- and low-intensity effort. And although findings (Vyazovskiy, 2015) suggest sleep loss can impair muscle recovery, there are no known studies investigating the potential interactions between sleep physiology and nutrition to optimize muscle recovery. Whey protein supplementation is likely important in enhancing performance, recovery, and body composition outcomes in these athletes, but limited trails have been conducted to date, and findings are inconsistent. Furthermore, it is unknown how this sports nutrition strategy would impact teenage athletes.

## Purpose and Objectives

---

The overall aim of the proposed project is to compare protein supplementation on performance, recovery, and body composition changes in adolescent soccer players between the whey protein and the control group in response to the 10-week intervention. Hypothesis: We hypothesize that the whey protein group will demonstrate more favorable changes in

performance, recovery, and body composition outcomes than the control group following the 10-week supplementation period.

Secondary outcomes will include investigating interactions between sleep physiology and dietary protein on muscle recovery and performance following the 10-week intervention.

*Hypothesis:* Sleep efficiency will be higher in the whey protein supplementation group versus the placebo control. *Exploratory* analyses will examine the impact of whey protein supplementation on dimensions of sleep including duration, regularity, satisfaction, alertness, timing, and sleep staging (e.g., stage N1, N2, SWS, rapid eye movement (REM))

The **expected outcomes** will provide support for whey protein supplementation to enhance exercise performance, recovery, and body composition in adolescent, team-sport athletes. Completion of the proposed objectives (see below) will add to the sparse evidence base on protein supplementation in this unique, athletic population, and provide preliminary data for future investigations in this area. Specifically, future work could address both mechanistic questions as well as evaluation of other protein options, such as milk consumption, which could be a more cost-effective and acceptable option for youth athletes.

Objective 1: Compare the impact of 10-weeks of whey protein vs. isocaloric control on performance in high school soccer players.

Objective 2: Compare the impact of 10-weeks of whey protein vs. isocaloric control on body composition in high school soccer players.

Objective 3: Compare the impact of 10-weeks of whey protein vs isocaloric control on hunger and satiety in high school soccer players

Objective 4: Compare the impact of 10-weeks of whey protein vs. isocaloric control on sleep duration and quality in high school soccer players.

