utilizing the track and field team was not a good scientific decision. Thus, we elected to conduct this study on adolescent soccer players.

**Travel to the University of Utah:** Travel via charter buses from Marsh Valley High School in Marsh Valley, ID to the University of Utah, and back to Marsh Valley will be provided free of charge to participants. We will utilize Salt Lake Express bus charter, which is the transportation provider for Marsh Valley High School athletics. The University of Utah's Risk Management Department does not have concerns with this transportation modality (see emails in Other Documents). The charter bus will be paid for utilizing grant funding awarded to the PI ([name]) from the study sponsor (Western Dairy Center).

**Pre-Intervention Procedures:** Before both testing days (pre- and post-intervention) we will ask that all participants record their diet and exercise for 2 days leading up to each of these visits. We will ask that they perform the same diet and activity behaviors that they report before the baseline intervention testing day for the post-intervention testing day. The morning of testing days, before departure from Marsh Valley High School, we will have them consume a study provided granola bar. The granola bar is a Chocolate Chip CLIF BAR® containing 250 calories. Allergens include soy, and may contain peanuts, tree nuts, milk, sesame, and wheat. Student-athletes will report to the Skeletal Muscle Exercise Research Facility in the morning, where they will undergo the following measures:

**Questionnaires:** Athletes will fill out gastrointestinal (GI) and sleep questionnaires. Specifically, the Munich Chronotype Questionnaire (MCTQ) (Shahid, Wilkinson, Marcu, & Shapiro, 2011), Pittsburg Sleep Quality Index (PSQI) (Smyth, 1999), a GI symptom questionnaire (Pereira, Dora IACouto Irving, Susana SLOmer, Miranda CE Powell, Jonathan J. 2014). Participants will fill out a 3-day, 24-hour ASA diet recall at baseline. This data will be uploaded to REDcap.

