**Anthropometrics and Body Composition Assessment:** In a private room, all athletes will undergo non-invasive measurements of height and weight (which will be used to calculate BMI-percentile) (Kuczmarski, 2002). Each athlete will next be measured for body composition via the BodPod. The BodPod requires participants to wear spandex-like material or a sport-style bathing suit for the body composition assessment. Participants will be required to change into these clothing materials as well as wear a swim cap to cover the hair (as is required for this equipment). They will change in a private bathroom that is located in the same private room where the BodPod is located. Importantly, the scale in which participants will have their weight measured on does not have a display. The weight is displayed only on the computer, which participants will not see. Participants will not be provided with their BodPod results, and will not be aware of their weight, BMI percentile, nor body composition. As it is done in private, no other participants will see other's weight or body composition either. Participant body composition and anthropometric forms will be printed at a later time by study staff and added to participant folders and our REDcap Data Set when participants have left.

**Blood Sample:** A blood sample will be obtained via the antecubital vein, by a trained member of the CTSI Clinical Services Core (CSC). The sample will consist of about a tablespoon of blood. We will use blood samples to measure the following biomarkers: IL-6, follistatin,

adiponectin, FGF21, decorin, and cathepsin B (CTSB)(Chow et al., 2022). IL-6 will be measured to assess systemic inflammation. Follistatin is measured to assess long-term muscle growth. Adiponectin is measured to assess inflammation. FGF21 is measured to assess the function of various metabolic pathways. Decorin is measured to assess inflammation. CTSB is measured to assess correlating protein levels in the blood. Blood samples will be centrifuged, and plasma samples will be stored in a -80-degree freezer for batch analysis at the end of the study. Study provided bagels will be distributed after the blood draw.

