## INTERVENTION:

In-season soccer practices and competition will occur 6-days per week across a 10- or 12-week period (pending soccer season length). During the 10- or 12-weeks, participants will consume their assigned supplement or placebo, every day, immediately after practice or competition (or midday on rest days), and immediately before bedtime. Participants will be alerted that it is time to consume their assigned product with a REDCap-delivered text message. Each dose will consist of 20g of whey protein, or 20g of isocaloric control, and will be mixed with 8oz of water in a shaker bottle, which participants will be provided with and will be able to keep at the end of the study. Participants will be provided with a random number of packets of products above the amount they need in order to evaluate compliance. Additionally, they will have a checklist in their bags to mark intake and if they accidentally lost any packets. Study personnel will distribute these bags at the beginning of each month. Participants will store all their empty containers in a separate provided bag, and each bag with

empty containers will be collected to track compliance by study personnel at the end of each month. Time points may vary by  $\pm 1$  week to allow for scheduling flexibility.

Sleep measures: Sleep measures will be evaluated as described above. Sleep measures will be collected at 2-, 4-, 6-, 8-, 10-, and potentially 12-weeks (pending soccer season length) and will be averaged at the end of each of the weeks listed.

Questionnaires: Participants will fill out a 3-day, 24-hour ASA diet recall at 5-, 10- and potentially 12-weeks (pending soccer season length). This data will be put into REDcap. Pittsburgh Sleep Quality Index (PSQI), DOMS questionnaire (Vickers, A. J. (2001)), and the GI symptom questionnaire will be completed at 2-, 4-, 6-, 8-, 10-, and potentially 12-weeks (pending soccer season length). Study personnel will send questionnaires to participants and will use REDCap to complete the questionnaires.

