Urine Samples: We will randomly assign participants to provide urine samples at weeks 4 and 8 as a sham adherence measure. These samples will be discretely disposed of following collection and will not be saved nor stored. We are using this method as a sham adherence measure so that participants will think that we can know if they are consuming their allotted supplement, which may help with their compliance. We will tell participants at the end of the study we did not take any measurements from their urine samples.

Post-testing will be the same as pre-testing and will commence after the 10- or 12-weeks (pending soccer season length). All measures described above in Pre-Intervention testing will take place again, with the exception of a week of Fitbit® monitoring following completion of the 10- or 12-week (pending soccer season length) intervention.

Debrief: Following completion of post-intervention testing, participants will be debriefed (see Debrief Document in Other Documents) regarding the sham urine collections which were used to increase adherence.

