### **Procedures performed for research purposes only:**

## **Statistical Methods, Data Analysis and Interpretation**

---

A two-way (group x time) repeated measures analysis of variance (ANOVA) will be used to compare change between groups in body composition, performance, and recovery. If a significance in group x time interactions occur, an independent t-test will be performed for each dependent variable between groups. An alpha level will be set at  $p < 0.05$ .

Sample size and power analysis: For a total of 60 participants, we anticipate a 30% attrition, leaving us with  $n=40$  ( $n=20$  per group). This provides  $>90\%$  power for detecting differences in our main outcome variables. Based on preliminary data, a similar study used  $n=18$  for their sample sizes. This sample size will be used for sample size calculations for a future well-

powered trial. Estimates for effect sizes will be implemented due to the limited sample size. Effect sizes ( $n^2$ ) will be defined as small (0.20), medium (0.50), and large (0.80).

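### Objective 3 compares hunger and satiety between arms, but the plan specifies no hunger or satiety measure at any time point and names no analysis for them

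*Combined protocol and SAP*

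**What the plan says.** Purpose and Objectives sets out four numbered objectives: performance, body composition, hunger and satiety, and sleep. The third reads "Compare the impact of 10-weeks of whey protein vs isocaloric control on hunger and satiety in high school soccer players".

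Under Procedures, the baseline questionnaires are introduced with "Athletes will fill out gastrointestinal (GI) and sleep questionnaires". The instruments then named are a chronotype questionnaire (MCTQ), a sleep quality index (PSQI) and a GI symptom questionnaire. Diet is covered by "Participants will fill out a 3-day, 24-hour ASA diet recall at baseline".

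During the season, the Intervention section schedules the PSQI and a soreness (DOMS) questionnaire, "and the GI symptom questionnaire will be completed at 2-, 4-, 6-, 8-, 10-, and potentially 12-weeks". For diet it says "Participants will fill out a 3-day, 24-hour ASA diet recall at 5-, 10- and potentially 12-weeks". Of post-testing it says "All measures described above in Pre-Intervention testing will take place again", apart from the week of Fitbit wear.

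The statistical section uses a group-by-time repeated measures ANOVA to "compare change between groups in body composition, performance, and recovery".

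**The concern.** An objective needs a measure, a time at which it is taken, and an analysis. Objective 3 has none of the three. Hunger and fullness felt during a 10- or 12-week season cannot be recovered once the season is over, so the gap can be closed only beforehand. If it stays open, the objective must either be dropped or be answered with a substitute, such as GI symptoms or recalled intake, chosen when the data are already in hand. A result of that second kind could not be presented as a planned comparison.

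**Working it through.** No formula applies and the plan gives no figure to reproduce. The check sets each listed assessment against Objective 3.

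**Baseline (Procedures)**
- Questionnaires: MCTQ, PSQI and GI symptoms. These concern chronotype, sleep quality and GI symptoms.
- Diet recall: reported intake.
- Height, weight and BodPod: body size and composition.
- Blood: IL-6, follistatin, adiponectin, FGF21, decorin and cathepsin B. Each is given a purpose, and none of those purposes is appetite. The marker a reader might most readily link to feeding has another role: "FGF21 is measured to assess the function of various metabolic pathways".
- 1.5-mile run, 30-yard sprint, leg strength and leg endurance: performance.
- Fitbit: sleep.

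**During the season (Intervention)**
- PSQI, DOMS and GI symptoms at weeks 2, 4, 6, 8, 10 and possibly 12.
- Diet recall at weeks 5, 10 and possibly 12.
- Fitbit sleep on the two-weekly schedule.
- Urine at weeks 4 and 8: a sham adherence device, discarded without measurement.

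**Post-test:** a repeat of the baseline battery without the Fitbit week, so it adds no new kind of measure.

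**Analysis (Statistical Methods, Data Analysis and Interpretation):** body composition, performance and recovery.

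**Count.** Measures designated for hunger or satiety: 0 at baseline, 0 during the season, 0 at post-test. Named analyses: 0. The two words occur only in Objective 3.

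**Comparison with the other objectives.** Objective 1 has the field and muscle tests, Objective 2 has the BodPod, and Objective 4 has the Fitbit and PSQI. Only Objective 3 has no identifiable instrument, which is 1 of 4.

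**Could something listed stand in?** The diet recall records what was eaten, not how hungry or full the athlete felt. There is a further weakness: participants are asked to repeat, before post-testing, the diet they recorded in the 2 days before baseline testing. If the week-10 recall falls on those days, reported intake is being steered back towards its baseline value. The GI questionnaire is presented only as a symptom tool. Neither instrument is linked to Objective 3.

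**The case against.** Four arguments can be made against the point.

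1. *The GI questionnaire may contain an appetite item.* A reader might infer from the list of instruments that no hunger or satiety data will be collected at all. The documents do not support that. The questionnaire is given at baseline, every two weeks and at post-test, and its items are not shown, so such an item cannot be excluded. This stands, and it limits the claim to what is specified. It does not rescue the objective: if the sponsor means to rely on such an item, the plan should name it, with its scoring and timing.

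2. *Related data are planned.* The diet recalls are prospective and longitudinal, so it would be wrong to say the trial gathers nothing that bears on eating. That stands too, but intake is at most an indirect proxy and is not assigned to this objective.

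3. *Absence from the ANOVA sentence proves little.* This is correct. Sleep is also missing from that sentence, yet sleep is clearly measured. The omission is a second gap, shared with Objective 4, and is not evidence that hunger goes unmeasured. The case rests on the list of assessments.

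4. *Objective 3 is peripheral.* Hunger and satiety do not appear in the overall aim, the hypotheses, the secondary or exploratory outcomes, or the power statement. A reader might infer that an unanswerable objective undermines the trial. It does not: no result on performance, recovery, body composition or sleep is biased or weakened by it. The objective is nevertheless numbered alongside the other three, and the same section says that completing the objectives will add to the evidence and supply preliminary data.

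**Conclusion.** The concern holds as an inconsistency between objectives and measures. One of four numbered objectives has no specified measure at any of the three stages and no named analysis, so it cannot be answered from the plan as written. The damage is confined to that objective.

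The conclusion rests on two assumptions. The first is that the Procedures and Intervention sections list all planned assessments. The second is that no companion form designates an appetite item. If such a form exists, the remedy reduces to citing it in the protocol and adding the analysis.

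**What to change.** Before the season starts, do one of the following.

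**Keep Objective 3.**
- Add brief hunger and fullness ratings to the REDCap questionnaires already sent every two weeks.
- Collect the baseline rating under the same conditions, for example at home by REDCap during the baseline Fitbit week and before the first supplement dose. The campus testing day is a poor choice, because athletes have by then eaten the study granola bar and receive bagels after the blood draw. A rating taken there would not be comparable with later ratings at home.
- State when the rating is made relative to meals and to supplement intake. A fixed clock time alone would not be enough, since intake is tied to practice or competition (midday on rest days) and to bedtime, so the interval from intake to rating would vary.
- Name one summary, such as the mean of the ratings during the intervention, and one between-arm analysis adjusted for baseline and for sex, the stratification factor. Other summaries would serve; what matters is that one is fixed in advance.

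**Or delete or reword Objective 3** so that it matches what is measured. If it becomes an objective about reported intake, say so and give that outcome its own analysis.

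The first route costs about one minute per questionnaire. With 1 baseline rating and 5 during the season (6 if week 12 is used), that is 1 + 5 = 6 to 1 + 6 = 7 ratings, or roughly 6 to 7 minutes per participant in all. Visits and sample size do not change. The second route costs one objective.

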## Study Population

---

**Age of Participants:** 13-18 years old

**Sample Size:**

At Utah:

All Centers: 60

**Inclusion Criteria:**

A total of 60 subjects are expected to enroll in this trial with a total of 40 completing the study protocol in its entirety to perform statistical analyses on our primary outcomes. We will recruit soccer players between the ages of 13-18 who are healthy, have no underlying metabolic diseases and have no contraindications to exercise.

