### **Procedures:**

**Informed Consent, Parental Permission and Assent:** These will be obtained over Zoom, prior to participation in any study procedures.

**Randomization:** Randomization will occur following pre-intervention testing. Participants will be randomized via random number generator stratified by sex, and blinded into either whey protein supplement group or placebo (isocaloric) control group.

**Pre- and Post-Intervention Testing Background:** Pre- and post-intervention testing will occur over a single day for each participant at the University of Utah campus. There will be three (3) separate days of pre-intervention and post-intervention testing. One day will be for members of the “Girls’ Soccer Team”. One day for members of the “Boys Soccer Team”. The final day will be a make-up day for participants who were unable to attend with their team, but wish to participate. According to the coaches, no student-athletes openly identify as non-binary nor transgender. However, in March of 2020 Idaho’s “Fairness in Women’s Sports Act” was signed in to law. While it has yet to go in to effect, if taken up, it will prohibit transgender women and girls from competing on teams that align with their gender identity in Idaho. Thus, it is possible that individuals may not be open about this. To address concerns re: outing anyone, participants will complete the testing day on their team’s assigned day, as mentioned above, or on the make-up day if they are not available on the main testing day. Furthermore, our strategy of having make-up testing options for both pre- and post-intervention means that not all members of each team will be tested on the same day. Thus, this mitigates potential risk of coercion as teammates will not know for sure who elected to participate or not in the trial.

**Selection of School:** Marsh Valley High School in Marsh Valley, ID was selected as the test site for this study due to the following connection:

The Track and Field coach at this school comes from a family of Dairy farmers and is also a Paralympic athlete who has had a relationship with the Western Dairy Center (study sponsor) for a number of years. He inquired with WDC about doing a trial on his student-athletes, so the WDC connected the PI ([name]) with this school for the trial. Due to large differences in athlete type and training load in track and field (sprinters, distance, jumpers, throwers),

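### The primary analyses appear to rest on about 40 completers of 60 enrolled athletes, with no all-randomised analysis set and no missing-data plan

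*Combined protocol and SAP*

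**What the plan says.** The Inclusion Criteria section states: "A total of 60 subjects are expected to enroll in this trial". The same sentence continues with "a total of 40 completing the study protocol in its entirety to perform statistical analyses on our primary outcomes". This is the only text that says whose data support the primary analyses.

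The section on statistical methods repeats the expectation as a sample-size forecast: "For a total of 60 participants, we anticipate a 30% attrition". It arrives at 40 athletes, 20 per group, and attaches its power claim to them. The method is: "A two-way (group x time) repeated measures analysis of variance (ANOVA) will be used to compare change between groups". Independent t-tests follow if the interaction is significant.

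On timing, the Randomization paragraph under Procedures says: "Randomization will occur following pre-intervention testing". It adds: "Participants will be randomized via random number generator stratified by sex". The supplement is then taken throughout the season: "In-season soccer practices and competition will occur 6-days per week across a 10- or 12-week period".

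The consent section lets participants withdraw at any time. No section says how the data of those who withdraw or stop the supplement are handled, or whether they are asked back for post-testing. The document defines no analysis set, missing-data method or sensitivity analysis.

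**The concern.** Full completion of the protocol is named as the basis for the primary analyses, and the chosen ANOVA also needs complete cases. A statistician who followed the text would therefore analyse completers. Completion is decided after allocation and could depend on it through taste, gastrointestinal tolerance, injury or fading performance. The protocol itself treats tolerance and adherence as live issues: it schedules gastrointestinal questionnaires every two weeks, counts packets, and uses a sham urine collection to encourage compliance.

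What is at stake is whether the whey and control groups being compared are still the groups that randomisation made alike. If different kinds of athlete leave the two arms, the estimated effect mixes the supplement with the selection.

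**Working it through.** **1. The plan's own figure.** 60 × (1 − 0.30) = 42, against the stated 40. In reverse, 40 / (1 − 0.30) = 57.1, so 58, against the stated 60. The ratio 40/60 implies a loss of 1 − 0.667 = 33.3%. The figures agree to within two athletes, so the forecast is reproduced and the rounding is not a problem in itself.

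**2. What the ANOVA drops, by outcome.**
- Body composition and performance are measured before and after only. With two time points, the group-by-time test is a t-test on change. An athlete without a post-test drops out, and there are no intermediate visits to miss.
- Soreness, PSQI, gastrointestinal symptoms and sleep are collected at weeks 2, 4, 6, 8 and 10, and at week 12 if the season runs that long. Here one missed occasion removes the athlete's other observations of that measure from a classical repeated-measures ANOVA.

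**3. How much a completers comparison could mislead.** From the documents: alpha 0.05, and about 40 of 60 retained in two equal groups. Assumed: all 60 randomised (30 per arm), one-third loss in each arm, pre-post correlation 0.7, unit SD at each time, no true effect, a two-sided test, and the dropout mechanisms below. Moderate and strong mean probit slopes of 0.5 and 1 per SD. There were 3,000 runs per row. The Monte Carlo standard error at 5% is √(0.05 × 0.95 / 3000) = 0.4 percentage points.

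| Loss depends on | Bias in change (SD) | Type I error, change | Type I error, ANCOVA |
|---|---|---|---|
| Nothing (random) | 0.00 | 4.7% | 5.5% |
| Poor change, same in both arms, strong | 0.00 | 4.6% | 4.6% |
| Poor change, one arm only, moderate | 0.19 | 11.8% | 10.0% |
| Poor change, one arm only, strong | 0.29 | 23.4% | 21.0% |
| Poor change in one arm, good change in the other, moderate | 0.37 | 33.6% | 29.2% |
| Low baseline, same in both arms, strong | 0.01 | 5.7% | 5.3% |
| Low baseline, one arm only, strong | −0.12 | 8.4% | 5.3% |
| Low baseline in one arm, high in the other, strong | −0.23 | 16.1% | 5.4% |

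A closed-form check for loss on poor change in one arm: bias = √(2(1 − ρ)) × b/√(1 + b²) × φ(z)/Φ(z). Here Φ(z) = 2/3, so z = 0.431 and φ(z)/Φ(z) = 0.3636/0.6667 = 0.545. With ρ = 0.7 the first factor is 0.775. Slope b = 0.5 gives 0.775 × 0.447 × 0.545 = 0.19. Slope b = 1 gives 0.775 × 0.707 × 0.545 = 0.30. The simulation gave 0.19 and 0.29.

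Two things follow. Equal numbers lost per arm do not protect the comparison, because every row loses one third from each arm. Baseline adjustment removes the bias when loss depends on baseline but only trims it when loss depends on the change itself. For that case the remedy is to obtain the post-tests.

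**4. What full follow-up could gain.** For a two-sided two-sample t-test at a standardised difference of 0.8, power is 69% with 20 per arm and 86% with 30 per arm. The difference detectable with 90% power falls from 1.05 to 0.85. This is an upper bound, since it needs all 60 randomised and post-tested.

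**The case against.** The strongest reply is that the plan never states a completers-only rule. The sentence on 40 completers is an enrolment forecast, and the attrition figure is what the investigators anticipate. Silence about the analysis set is not the same as a decision to exclude. That is right, and it is why the point says the plan appears to rest on completers. It does not remove the gap, because neither the text nor the named method leads anywhere else.

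Several stronger readings are tempting and are not supported:
- A reader might infer that a third of randomised athletes will be excluded. The 60 are enrolled, randomisation follows pre-testing, and the stated attrition is 30%. Some loss may come before allocation.
- A reader might compound missed visits on top of the 40. Those 40 are described as completing everything, so the two losses cannot be stacked. Per-visit missingness is also irrelevant to outcomes measured only before and after.
- A reader might infer that a missed urine sample would cost an athlete a place in the analysis. No such rule exists, and the samples are discarded unmeasured.
- A reader might treat week 12 as individual missing data. It depends on season length at one school, so it would generally exist for a whole team or not at all. What remains is that the last time point is not fixed in advance.

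Two further objections carry weight. The plan also describes its sample as informing a future, better-powered trial, which lowers the stakes somewhat, although it claims more than 90% power for its main outcomes. And a mixed model recovers little for an athlete with no post-test.

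**Conclusion.** The concern holds as a gap in the plan with a conditional consequence. As written, the plan leads to a comparison of about 40 of 60 enrolled athletes chosen by completion, with nothing to restore the protection of randomisation.

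Bias is possible but not shown. If loss is random, or related to outcome equally in both arms, type I error stays near 5%. If loss follows poor change in one arm only, the illustration gives a bias of 0.19 to 0.29 SD and a type I error of 12% to 23%. Dependence in opposite directions gives 34%. These sizes rest on the assumed correlation, loss rate and dropout mechanisms, none of which the documents supply. It would go too far to say that the comparison is no longer randomised, since the loss is forecast and its relation to arm is unknown.

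**What to change.** 1. Define the primary analysis set as all randomised athletes in their assigned arm, regardless of compliance. State that those who stop the supplement are still invited to post-testing.
2. For body composition and performance, replace the group-by-time ANOVA and follow-up t-tests with one baseline-adjusted model (ANCOVA or a constrained-baseline mixed model) that includes sex, the stratification factor.
3. For soreness, PSQI, gastrointestinal symptoms and sleep, use a likelihood mixed model on all available observations, with group, time, their interaction and sex. Fix the last common time point in advance. Include baseline where it is collected; soreness is not among the baseline questionnaires listed.
4. Report completers as a sensitivity analysis. Add one that departs from missing-at-random, since baseline adjustment does not cure loss that depends on unobserved change.

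The analysis changes cost SAP wording and standard software. The real cost is in step 1: post-testing takes place on the University of Utah campus, so each extra post-test means contact effort and travel. The mixed model relies on missing-at-random, and little is gained for athletes who provide no post-test data.
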